## 4.2 Exclusion Criteria

### 4.2.1 Pregnancy or Breast-Feeding

Pregnant or breast-feeding women will not be entered on this study due to risks of fetal and teratogenic adverse events as seen in animal studies. Pregnancy tests must be obtained in girls who are post-menarchal. Males or females of reproductive potential may not participate unless they have agreed to use an effective contraceptive method, while receiving study treatment and for 3 months after the last dose of erdafitinib. Male subjects (with a partner of child-bearing potential) must use a condom with spermicide when sexually active and must not donate sperm from the first dose of study drug until 3 months after the last dose of study drug.

### 4.2.2 Concomitant Medications

4.2.2.1 Corticosteroids: Patients receiving corticosteroids who have not been on a stable or decreasing dose of corticosteroid for at least 7 days prior to enrollment are not eligible. If used to modify **immune adverse events** related to prior therapy,  $\geq$  14 days must have elapsed since last dose of corticosteroid (See [Section 4.1.6.1.d](#)).

4.2.2.2 Investigational Drugs: Patients who are currently receiving another investigational drug are not eligible.

4.2.2.3 Anti-cancer Agents: Patients who are currently receiving other anti-cancer agents are not eligible.

#### 4.2.2.4 Anti-GVHD agents post-transplant:

Patients who are receiving cyclosporine, tacrolimus or other agents to prevent graft-versus-host disease post bone marrow transplant are not eligible for this trial.

4.2.2.5 CYP3A4 Agents: Patients who are currently receiving drugs that are strong inducers or inhibitors of CYP3A4 are not eligible. See [Appendix](#)

[II](#) for a list of agents. Note: CYP3A4 inducing anti-epileptic drugs and dexamethasone for CNS tumors or metastases, on a stable dose, are allowed.

4.2.2.6 CYP2C9 Agents: Patients who are currently receiving drugs that are strong inducers or moderate inhibitors of CYP2C9 are not eligible. See [Section 7.5.2](#).

- 4.2.3 Infection: Patients who have an uncontrolled infection are not eligible.
- 4.2.4 Patients who have received a prior solid organ transplantation are not eligible.
- 4.2.5 Patients who in the opinion of the investigator may not be able to comply with the safety monitoring requirements of the study are not eligible.
- 4.2.6 A history of cardiovascular diseases: Unstable angina, myocardial infarction, or known congestive heart failure Class II-IV within the preceding 12 months; cerebrovascular accident or transient ischemic attack within the preceding 3 months, pulmonary embolism within the preceding 2 months.
- 4.2.7 A history of any of the following: sustained ventricular tachycardia, ventricular fibrillation, Torsades de Pointes, cardiac arrest, Mobitz II second degree heart block or third degree heart block; known presence of dilated, hypertrophic, or restrictive cardiomyopathy.
- 4.2.8 Uncontrolled intercurrent illness including, but not limited to, ongoing or active infection, symptomatic congestive heart failure, unstable angina pectoris, cardiac arrhythmia, or psychiatric illness/social situations that would limit compliance with study requirements.
- 4.2.9 Patients with significant ophthalmologic conditions (uncontrolled glaucoma, central serous retinopathy, history of retinal vein occlusion or retinal detachment, excluding patients with longstanding findings secondary to existing conditions) are not eligible, to be confirmed with baseline ophthalmologic exam. All patients must have a baseline ophthalmologic exam, including funduscopy to confirm no significant ophthalmologic conditions are present.

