### **Potential Drug Interactions**

Erdafitinib is a weak time-dependent inhibitor and weak inducer of CYP3A4. Until further data become available, concomitant use of erdafitinib with CYP3A4 substrates with narrow therapeutic indices should be avoided.

Co-administration with a moderate CYP2C9 or strong CYP3A4 inhibitor increased erdafitinib exposure and may lead to increased drug-related toxicity. The use of moderate inhibitors of CYP2C9 and strong inhibitors of CYP3A4 are not permitted for the duration of the study.

The impact of strong CYP2C9 or CYP3A4 inducers (such as rifampin) on erdafitinib was not clinically studied. The concomitant use of strong CYP2C9 and CYP3A4 inducers with erdafitinib should be avoided as co-administration may significantly decrease erdafitinib exposure. Caution should be exercised for concomitant administration of erdafitinib and moderate CYP2C9 or CYP3A4 inducers as this may result in decreased erdafitinib exposure.

Co-administration of erdafitinib with other serum phosphate altering agents may affect serum phosphate concentrations. Avoid co-administration of serum phosphate altering agents if reasonable alternatives exist.

Concomitant administration of erdafitinib with P-glycoprotein (P-gp) substrates may increase their systemic exposure if administered concurrently. Oral narrow therapeutic index P-gp substrates such as digoxin should be taken at least 6 hours

before or after erdafitinib to minimize the potential for interactions.

Erdafitinib was shown to be an OCT2 inhibitor in vitro. PK simulations with metformin, an OCT2 substrate, predicted a lack of clinically relevant interaction with erdafitinib. However, until further data are available, consider alternative therapies that are not OCT2 substrates.

No clinically significant QT prolongation or cardiovascular effects have been noted to date. Clinical trials revealed no effects of erdafitinib on cardiac repolarization or other electrocardiographic parameters.

Acid lowering agents (e.g., antacids, H2-antagonists, or proton pump inhibitors) are not expected to affect the bioavailability of erdafitinib. Erdafitinib may be co-administered with an acid lowering agent.

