**11.8 Correlative Studies**

A descriptive analysis of pharmacokinetic (PK) parameters will be performed to define systemic exposure, drug clearance, and other pharmacokinetic parameters. The PK parameters will be summarized with simple summary statistics, including means, medians, ranges, and standard deviations (if numbers and distribution permit).

A descriptive analysis of the exploratory aims described in [Section 1.3](#) will be performed and will be summarized with simple summary statistics. All of these analyses will be descriptive in nature.

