**APPENDIX II: CYP3A4 SUBSTRATES, INDUCERS AND INHIBITORS**

This is not an inclusive list. Because the lists of these agents are constantly changing, it is important to regularly consult frequently updated medical references.

CYP3A4 substrates	Strong Inhibitors	Moderate Inhibitors	Strong Inducers	Moderate Inducers
acalabrutinib 	atazanavir	aprepitant	barbiturates	bosentan
alfentanil 	boceprevir	conivaptan	carbamazepine	dabrafenib
amiodarone 	clarithromycin	crizotinib	enzalutamide	efavirenz
aprepitant/fosaprepitant	cobicistat	diltiazem	fosphenytoin	etravirine
atorvastatin	darunavir	dronedarone	phenobarbital	modafinil
axitinib	delavirdine	erythromycin	phenytoin	nafcillin
bortezomib	grapefruit 	fluconazole	primidone	rifapentin
bosutinib 	grapefruit juice 	fosamprenavir	rifampin	
budesonide 	idelalisib	grapefruit 	St. John's wort	
bupirone 	indinavir	grapefruit juice 		
cabozantinib	itraconazole	imatinib		
calcium channel blockers	ketoconazole	isavuconazole		
cisapride	lopinavir/ritonavir	mifepristone		
citalopram/escitalopram	nefazodone	nilotinib		
cobimetinib 	nelfinavir	verapamil		
conivaptan 	posaconazole			
copanlisib	ritonavir			
crizotinib	saquinavir			
cyclosporine 	telaprevir			
dabrafenib	telithromycin			
dapsone	voriconazole			
darifenacin 				
darunavir 				
dasatinib 				
dexamethasone 				
diazepam				
dihydroergotamine				
docetaxel				
doxorubicin				
dronedarone 				
eletriptan 				
eplerenone 				
ergotamine 				
erlotinib				
estrogens				
etoposide				

everolimus  fentanyl  gefitinib haloperidol ibrutinib  idelalisib imatinib indinavir  irinotecan isavuconazole  itraconazole ivacaftor ketoconazole lansoprazole lapatinib losartan lovastatin  lurasidone  macrolide antibiotics maraviroc  medroxyprogesterone methadone midazolam  midostaurin  modafinil nefazodone nilotinib olaparib ondansetron osimertinib paclitaxel palbociclib pazopanib quetiapine  quinidine  regorafenib romidepsin saquinavir  sildenafil  simvastatin 				
---	--	--	--	--

sirolimus 				

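### The inducer rules in 4.2.2.5, 4.2.2.6, 7.5 and 9.1.1 need reconciling, and 11.8 should report PK with and without concomitant inducers

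*Combined protocol and SAP*

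**What the plan says.** **CYP3A4.** Section 4.2.2.5 sets the rule: "Patients who are currently receiving drugs that are strong inducers or inhibitors of CYP3A4 are not eligible". It then adds an exception: "CYP3A4 inducing anti-epileptic drugs and dexamethasone for CNS tumors or metastases, on a stable dose, are allowed". Section 7.5.1 carries both into the treatment period. Appendix II, to which both sections refer, places "carbamazepine" in its strong-inducer column together with fosphenytoin, phenobarbital, phenytoin, primidone and barbiturates. Its moderate-inducer column contains no anti-epileptic. Dexamethasone appears only among the substrates.

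**CYP2C9.** Section 4.2.2.6 says: "Patients who are currently receiving drugs that are strong inducers or moderate inhibitors of CYP2C9 are not eligible". Section 7.5.2 repeats the bar for patients on study. Neither section mentions anti-epileptics or names any agent, and Appendix II covers CYP3A4 only.

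**Drug information.** Section 9.1.1 (Potential Drug Interactions) says: "The concomitant use of strong CYP2C9 and CYP3A4 inducers with erdafitinib should be avoided as co-administration may significantly decrease erdafitinib exposure". It makes no exception for anti-epileptics. Just before that it says: "The impact of strong CYP2C9 or CYP3A4 inducers (such as rifampin) on erdafitinib was not clinically studied".

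**PK analysis.** Aim 1.2.3 is secondary and seeks preliminary pediatric estimates. Sampling is optional and takes place on Days 1 and 2 of Cycle 2 (8.4). Section 11.8 says: "The PK parameters will be summarized with simple summary statistics, including means, medians, ranges, and standard deviations", where numbers and distribution allow. Neither 11.8 nor 8.4 provides a split, an exclusion or a sensitivity analysis by inducer use.

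**The concern.** Two things do not fit together.

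First, sites get three statements about the same drugs: an exception in the CYP3A4 criterion, a CYP2C9 criterion without that exception, and drug-information text that advises against strong inducers of either enzyme. Section 4.0 says the criteria are applied to the letter and without waiver, so a site needs to know how they combine.

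Second, the protocol names a factor that it expects to lower exposure, admits patients who carry it, and then plans PK summaries that ignore it. Section 2.3.1 records no earlier pediatric experience, the dose is scaled from adults by body surface area, and 11.2 foresees that a later pediatric study may have to refine it. Readers will therefore look to these estimates. Both glioma grades, ependymoma and medulloblastoma are target histologies in Appendix VII, so patients who use the exception are foreseeable. An undivided summary would mix two clearance populations. It would describe the enrolled mix correctly but misdescribe children not taking an inducer.

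**Working it through.** **1. Does the exception admit strong inducers?** Section 4.2.2.5 excludes only strong CYP3A4 inducers. An exception to it therefore has effect only for strong ones, and every anti-epileptic in Appendix II's inducer columns is in the strong column. So yes, as far as the CYP3A4 criterion goes.

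**2. Is there a plan figure to reproduce?** Not for PK, since no PK sample size or precision target is stated. As a check on the primary design, at least 3 responses in 20 gives exact alpha 0.0755 at a 5% response rate and power 0.909 at 25%. This agrees with the 10% and 90% in 11.3, and nothing here touches it.

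**3. Inputs.**
- f = 0.20, the CYP3A4 share of clearance (9.1.1, Pharmacokinetics), read as a share of the total.
- Between-patient CV of 30% to 50% for Cmax and AUC in adults with cancer (2.2.1).
- k, the fold-induction of CYP3A4 clearance: not in the documents, assumed 2 to 5.
- q, the share of PK patients on an inducer: not in the documents, assumed 10% to 30%.

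**4. Formulas.** Clearance ratio in an induced child R = 1 + f(k − 1). AUC ratio = 1/R. Change in mean AUC over all sampled patients = q(1/R − 1). Change in mean clearance = q(R − 1). Both changes are relative to children not on inducers.

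| k | R | AUC, induced child | Mean AUC, q = 10% / 20% / 30% | Mean clearance, q = 10% / 20% / 30% |
|---|---|---|---|---|
| 2 | 1.2 | −17% | −1.7% / −3.3% / −5.0% | +2% / +4% / +6% |
| 3 | 1.4 | −29% | −2.9% / −5.7% / −8.6% | +4% / +8% / +12% |
| 5 | 1.8 | −44% | −4.4% / −8.9% / −13.3% | +8% / +16% / +24% |

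If the 20% is instead a share of the 67% of clearance that is metabolic, f = 0.20 × 0.67 = 0.134. The fall per induced child is then 1 − 1/1.134 = 12% at k = 2 and 1 − 1/1.536 = 35% at k = 5.

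**5. Spread of clearance.** Assume the same CV, c, in both groups. Relative to the non-induced mean, the variance over all patients is (1 − q)c² + q(cR)² + q(1 − q)(R − 1)², and the mean is 1 + q(R − 1).
- q = 0.10, R = 1.2, c = 0.30: variance 0.081 + 0.0130 + 0.0036 = 0.0976; CV = 0.312/1.02 = 31%.
- q = 0.30, R = 1.8, c = 0.30: variance 0.063 + 0.0875 + 0.1344 = 0.2849; CV = 0.534/1.24 = 43%.

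So a true CV of 30% would be reported as about 31% to 43%.

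**6. Comparison with sampling error.** The standard error of a mean, as a percentage, is CV/√n. At n = 20 it is 30/√20 = 6.7% to 50/√20 = 11.2%. At n = 5 it is 13.4% to 22.4%. The shift in mean AUC of 1.7% to 13.3% thus runs from negligible to about one standard error.

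**The case against.** The strongest reply is that the exception is deliberate. It is stated twice in the operative sections and limited to a stable dose. Section 9.1.1 says the named inhibitors are not permitted, but uses softer, advisory wording for strong inducers, so a narrow exception can coexist with it. The PK aim is preliminary, descriptive and based on optional sampling, and no decision depends on it. All of this stands. It lowers the stakes, but it does not give sites one consistent statement or make an undivided summary the better report.

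A reader might go further in several ways that the documents do not support:
- **That 4.2.2.5 and 4.2.2.6 flatly contradict each other for a given anti-epileptic.** Criteria apply jointly, so an exception to one does not waive the next, and the documents name no CYP2C9 inducer. What is shown is a missing list and a missing cross-reference.
- **That the effect matches or exceeds between-patient variability.** The 17-44% fall is per induced child. It starts below the 30-50% CV and stays inside it at the top. Adding a doubling of CYP2C9 clearance would give larger falls, but strong CYP2C9 inducers are already excluded.
- **That lower exposure in CNS patients would go unseen.** The diary (Appendix III-A) asks for other drugs taken. Serum phosphate, which 2.2.1 describes as exposure-related, is measured weekly in Cycle 1 and before later cycles.
- **That dexamethasone users are induced patients.** Appendix II lists it only as a substrate.
- **That a planned comparison with adult exposure is spoiled.** Neither 8.4 nor 11.8 plans one.

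**Conclusion.** The point holds in a limited form. The inducer passages need reconciling by the sponsor. PK reported without regard to inducer use could understate exposure, and overstate clearance and its spread, in children not on inducers. The direction follows from 9.1.1. The size is unknown, because the effect was not clinically studied and the number of such children is not given.

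Under the assumed 2- to 5-fold CYP3A4 induction and 10-30% of PK patients on inducers, mean AUC shifts by about −2% to −13% and mean clearance by +2% to +24%. That mixing follows from the silence of 11.8, which does not say that patients on inducers will be combined with the rest. It would be too strong to call the PK aim invalid. This is an inexpensive improvement to a preliminary secondary analysis, and the primary response rule is unaffected.

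**What to change.** 1. The sponsor should reconcile 4.2.2.5, 4.2.2.6, 7.5.1, 7.5.2 and 9.1.1 so that one statement covers inducing anti-epileptics for both enzymes, and should give sites the agents meant by the CYP2C9 rule. Which rule applies is the sponsor's clinical decision.
2. In 11.8, pre-specify that PK parameters are reported overall and separately for patients with and without a concomitant CYP3A4 or CYP2C9 inducer at Cycle 2 Day 1.
3. State whether dexamethasone counts as an inducer for this split.
4. Confirm that the Pharmacokinetic Study Form (8.4.5) or the diary records inducer use on the sampling day. The form's contents are not in the protocol, so this is a request to confirm and not a finding that a field is missing.

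The cost is some wording, one extra table split and possibly one form field. The downside is small subgroups, perhaps too small for more than individual listings. Keeping the overall summary means that no patient is lost from it. Sample size and the decision rule do not change.

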## 5.0 TREATMENT PROGRAM

### 5.1 Overview of Treatment Plan

Treatment Schedule Table	
Days 1-28	4.7 mg/m  erdafitinib once daily, with maximum of 8 mg per day
Day 28	Evaluation

Erdafitinib tablets will be given orally once daily. A cycle of therapy is considered to be 28 days. A cycle may be repeated up to a total duration of therapy of 2 years (maximum 26 cycles). **On Day 1 of Cycle 2, the dose of erdafitinib should be held until a pre-dose plasma sample can be obtained. In order to obtain the 24-hour time point, the dose on Day 2, Cycle 2 should also be held until plasma sample is obtained.**

**Erdafitinib is provided by NCI. Do not use commercial supply.**

Therapy will be discontinued if there is evidence of progressive disease or drug related dose-limiting toxicity that requires removal from therapy ([Section 6.0](#)). Therapy may otherwise continue for up to 2 years (maximum 26 cycles) provided the patient meets the criteria for starting subsequent cycles ([Section 5.2](#)) and does not meet any of the criteria for removal from protocol therapy criteria ([Section 10.0](#)).

Drug doses should be adjusted based on the BSA calculated from height and weight measured within 7 days prior to the beginning of each cycle, and according to the dosing nomogram (see [Appendix IV](#)). If vomiting occurs within 30 minutes of erdafitinib administration, then the dose can be repeated once. If a dose is missed, it can be taken up to 6 hours after the scheduled time. If it has been more than 6 hours since the missed dose, then that dose should be skipped. The next dose should be taken at the usual time

Please refer to [Section 7.3](#) for specific supportive care guidelines.

Since the adult RP2D (8 mg PO once daily) is below the MTD (at least 12 mg PO once daily) the starting dose as per standard Pediatric MATCH routine (described in additional detail in [Section 11.2.1](#) of the screening protocol APEC1621SC) will be the adult RP2D adjusted for BSA, which is 4.7 mg/m^2/day (8 mg/1.7 m^2) up to a maximum daily dose of 8 mg PO once daily.

**5.1.1 Therapy Delivery Map**

See [Appendix V](#) for therapy delivery map for Cycle 1 and subsequent cycles.

**5.1.2 Intra-Patient Escalation**

Inpatient dose escalation is not allowed.

**5.2 Criteria for Starting Subsequent Cycles**

A cycle may be repeated every 28 days if the patient has at least stable disease and has again met laboratory parameters as defined in the eligibility section, [Section 4.0](#) and eligible to continue agent administration per the requirements in [Section 6.0](#).

**5.3 Grading of Adverse Events**

Adverse events (toxicities) will be graded according to the current version of the NCI Common Terminology Criteria for Adverse Events (CTCAE). All appropriate treatment areas should have access to a copy of the current version of the CTCAE V5.0. A copy of the CTCAE V5.0 can be downloaded from the CTEP website (<http://ctep.cancer.gov>). Any suspected or confirmed dose-limiting toxicity should be reported immediately (within 24 hours) to the Study Chair.

**5.4 Definition of Dose-Limiting Toxicity (DLT)**

DLT will be defined as any of the following events that are possibly, probably or definitely attributable to protocol therapy. Dose limiting hematological and non-hematological toxicities are defined differently.

**5.4.1 Non-Hematological Dose-Limiting Toxicity**

- 5.4.1.1 Any Grade 3 or greater non-hematological toxicity attributable to the investigational drug with the specific exclusion of:
- Grade 3 nausea and vomiting of < 3 days duration
  - Grade 3 liver enzyme elevation, including ALT/AST/GGT that returns to

levels that meet initial eligibility criteria or baseline within 7 days. See [Section 6.3](#), and [Appendix XI](#) for values that represent thresholds between CTCAE grades.

Note: For the purposes of this study the ULN for ALT is defined as 45 U/L regardless of baseline.

- Grade 3 or 4 fever < 5 days duration.
- Grade 3 infection < 5 days duration.
- Grade 3 hypophosphatemia, hypokalemia, hypocalcemia or hypomagnesemia responsive to supplementation

5.4.1.2 Any Grade 1 visual disturbance that persists for  $\geq 4$  weeks

5.4.1.3 Any Grade 2 non-hematological toxicity that persists for  $\geq 7$  days and is considered sufficiently medically significant or sufficiently intolerable by patients that it requires treatment interruption.

Note: Allergic reactions that necessitate discontinuation of study drug will not be considered a dose-limiting toxicity.

5.4.1.4 Hyperphosphatemia will be reported as a DLT if a dose modification is required (as described in [Section 6.4](#) for serum phosphate of 7.0 or greater)

#### 5.4.2 Hematological dose limiting toxicity

5.4.2.1 Hematological dose limiting toxicity is defined as:

- a) In patients evaluable for hematological toxicity (see [Section 4.1.7.1](#)),
- Grade 4 thrombocytopenia or neutropenia, not due to malignant infiltration.
  - Grade 3 thrombocytopenia that persists for  $\geq 7$  days
  - Grade 3 thrombocytopenia requiring a platelet transfusion on two separate days within a 7-day period
  - Grade 3 thrombocytopenia with clinically significant bleeding
  - Neutropenia or thrombocytopenia that causes a delay of > 14 days between treatment cycles (e.g. platelets < 100K/mm^3 or ANC < 1000/mm^3).

5.4.2.2 Note: Grade 3 or 4 febrile neutropenia will not be considered a dose-limiting toxicity.

## 6.0 DOSE MODIFICATIONS FOR ADVERSE EVENTS

**The Study Chair must be notified of any dosage modification or use of myeloid growth factor.**

### 6.1 Dose Modifications for Hematological Toxicity

6.1.1 If a patient experiences hematological toxicity as defined in [Section 5.4.2](#), the treatment will be held. Counts should be checked every 3-4 days for thrombocytopenia and every other day for neutropenia during this time. If the toxicity resolves to meet eligibility parameters within 14 days of drug discontinuation, the patient may resume treatment at a reduced dose as outlined in the dosing nomogram table in [Appendix IV](#). Doses reduced for toxicity will not be re-escalated, even if there is minimal or no toxicity with the reduced dose.

- 6.1.2 If toxicity does not resolve to meet eligibility parameters within 14 days of drug discontinuation, the patient must be removed from protocol therapy.
- 6.1.3 If hematological dose-limiting toxicity recurs in a patient who has resumed treatment at the reduced dose, the patient must be removed from protocol therapy.

